2.2 Secondary aims

Quantitatively, we aim at assess the activity of the CEC and its diffusions, knowledge and utilization among HPs, while qualitatively, the opinions/perspectives on it from users and providers health professionals in terms of barriers/facilitators, expectations and needs.

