Then, the study has several components and includes data from different stakeholders of the CEC (HPs, CEC's members, Managers and Heads of Departments), as reported in the following table:

Evaluating a Clinical Ethics Committee (CEC) implementation process in an Oncologic Research Hospital. A process evaluation study using Normalization Process Theory .

Table 1. Data sources in the project and the main topics they address

Outcome	Type of data	Data collection	Population
Evaluation of CEC's structure - 'top down' approach			
To quantify -the amount of activities performed by CEC in 16 months; - the amount of resources required by the CEC; To assess: - how much the CEC worked; - how much CEC has been used by HPs	Quantitative	Internal database	-
To explore the opinion on CEC functioning, role within the health care facility and expectation	qualitative	Semi-structured interview	Managers/Heads who formally supported and promoted the intervention
To explore the opinion on CEC functioning, role within the health care facility and expectation	qualitative	Semi-structured interview	CEC's members
Evaluation of CEC's activities - 'bottom up' approach			
To assess spread, use and knowledge of CEC among HPs in terms of: -knowledge; -spread within health care facility -access -reception of activities provided by the CEC (training, EC, policy guideline) -interest to the service -eventual impact of policy guideline developed by CEC on clinical practice	quantitative	Anonymous survey	All HPs employed at the Health care Authority of Reggio Emilia.
To explore opinions from HPs on: -comprehension of the CEC role; -utility of the service, -expectations and needs; -barriers and facilitators;	Qualitative and quantitative	Cognitive survey	HPs who participated to the training on ethics consultation provided by the CEC
To explore the experience with EC provided by CEC	qualitative	Semi-structured interview	HPs who submitted an ethics consultation request

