Personal interviews will be held via video teleconference (Lifesize system) or in presence, audio-recorded and transcribed in full.

Recruitment Procedure (cognitive survey)

All the HPs who registered to 1 of the 5 training course on ethics consultation will be recruited from the database of the Training Office. To guarantee HPs' anonymity, the PI will contact the Head of the Training Office who, on behalf of the PI, will sent an email to all the HPs attended the course. Since any further contact will be between the PI and the Head of the training office, it will not possible for the PI to identify who answer the survey. The email will contain all the information related to the study's objectives and a link to the online

Evaluating a Clinical Ethics Committee (CEC) implementation process in an Oncologic Research Hospital. A process evaluation study using Normalization Process Theory .

survey and it also specifies that any personal data will be required to fulfill the survey, which will be completely anonymous.

Participants are expected to submit the survey in two weeks from the first invitation. Then a reminder will be sent to submit responses within another week.

Data collection

Semi-structured interview

The semi-structured interview is a social interaction between two subjects: the interviewer and the interviewee. It has a cognitive purpose with the primary purpose of collecting data. The semi-structured interview guide includes a series of questions that must be asked to all interviewees without the need for a pre-established order, leaving space for any further investigation.

It will be the interviewer's concern to create a climate based on non-judgmental listening and mutual trust (Bichi 2007, Cocci 2005).

Therefore, the interviews will be conducted by the members of the research team, who have received special training in this regard and the place of the interview will be by the selected participating members.

The expected duration of the interview is between 30 and 50 minutes; the interview will be audio-recorded.

Interview's topic guide are informed by NPT four concepts.

Table 3: topic of Interviews' topic guide accordingly with NPT core concepts

concept	Key attribute	Topics of the interview are:
Coherence	Sense-making	motivations/ expectations to implement the CEC and understanding of its role within the Health Care Facility
Cognitive participation	engagement	understanding of personal commitment to the service

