Appendix 1 Interview's topic guide

Coherence of the CEC	What is the process?	how participants who benefitted from CEC's activities perceive the CEC and whether they experienced the CEC as valuable to them and agreed about its usefulness and purpose.
Cognitive participation	Who performs the process?	whether participants saw the CEC as a legitimate part of their work and whether they supported it over time
Collective action	(How is the process performed?)	how the CEC was provided within the existing context, how the embedding and integration had proceeded, and what factors promoted or inhibited the work
Reflexive monitoring	(How is the process understood?)	how participants individually and collectively evaluate the CEC

The semi-structured interview with the Managers/Department Heads who promoted the intervention will reflect the following themes:

- A. Perception of the role of CEC in the local context, and motivations behind the implementation of CEC.
- B. Understanding of their own activities in support of CEC.
- C. Understanding the strengths and critical aspects related to the service
- D. Reflection on their perceived impact in the local context

Opening

Good morning, thank you for the time you dedicated to participate in this study. Regarding the purpose of the research, do you have any questions or concerns to clarify? Is it clear to you why we are here?

-Would you like to tell me what was your experience with Clinical Ethics Committee (CEC)?

Topic A - coherence :

-In your opinion, what is the role of the CEC within the Local healthcare Authority?

-How, in your opinion, is it different from other services and what is its specificity?

-What is the goal of the CEC and how does it act in the local context?

-Are there any motivations that prompted you to support/promote this service?

Evaluating a Clinical Ethics Committee (CEC) implementation process in an Oncologic Research Hospital. A process evaluation study using Normalization Process Theory .

Theme B - cognitive participation

-How do you help promote to this service?

-What do you think about the value of a service like CEC to your work and your colleagues?

Topic C - collective action

-Thinking about the activities carried out by the CEC, how have they been integrated into the local context?

-Were there any limitations (organizational? Internal? External to the service? Economic?) that you perceive with respect to the CEC? If yes, which ones?

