-Were there potentials instead with respect to the service that was implemented? If yes, which ones?

Topic D - reflexive monitoring

-Considering what has been done in these 16 months, how do you evaluate the service?

- In what ways could the CEC be improved?

Conclusion

Do you have any additional thoughts, examples, comments to share?

Evaluating a Clinical Ethics Committee (CEC) implementation process in an Oncologic Research Hospital. A process evaluation study using Normalization Process Theory .

The semi-structured interview with CEC's members will reflect on the following themes:

- A. Perception of the CEC's role in the local context and motivations for participating in it
- B. Understanding of their own activities in support of the CEC
- C. Understanding of strengths and critical issues related to the service
- D. Reflection on service use and perception of the impact produced in the local context

Opening

Good morning, thank you for your willingness to participate in this study. Regarding the purpose of the research, do you have any questions or concerns to clarify? Is it clear to you why we are here?

1. Would you like to tell me about your experience with the CEC?

Topic A - coherence

- In your opinion, what is the role of the CEC within the local Health Care Authority?
- How, in your opinion, is it different from other services and what is its specificity?
- What is the goal of the CEC and how does it act in the local context?
- What are your motivations for taking part in this service?

Theme B - cognitive participation.

- What does your work in this service consist of?
- What do you think about the value of a service like the CEC to your work and to your colleagues?

Theme C - collective action

- Thinking about the activities carried out by the CEC, how were they integrated into the local context?
- Were there any limitations (organizational? Internal? External to the service? Economic?) that you perceive with respect to the CEC? If yes, which ones?
- Were there strengths with respect to the service that was implemented? If yes, which ones?

Topic D - reflexive monitoring

- In light of what has been done in these 16 months, how do you evaluate the implemented service?
- In what ways could the CEC be improved?

Conclusion

Do you have any additional thoughts, examples, comments to share? Are there any important things that did not come up during the interview?

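### The manager and CEC-member interview guides contain no question on expectations, although the plan makes expectations a topic of those interviews

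*Combined protocol and SAP*

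**What the plan says.** Section 2.2 (Secondary aims) sets the qualitative objective as "the opinions/perspectives on it from users and providers health professionals in terms of barriers/facilitators, expectations and needs". The introduction to the Qualitative Evaluation repeats it.

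The table of data sources under The evaluation study (the second table numbered 1) assigns topics to each source. The rows for managers/heads and for CEC members carry the same text: "To explore the opinion on CEC functioning, role within the health care facility and expectation". The row for professionals who requested a consultation is different: "To explore the experience with EC provided by CEC". The cognitive-survey row, for professionals who attended CEC training, does list expectations.

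Table 3, which links interview topics to the four NPT concepts, describes Coherence as "motivations/ expectations to implement the CEC and understanding of its role within the Health Care Facility".

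On the status of the guides, the Semi-structured interview section states: "The semi-structured interview guide includes a series of questions that must be asked to all interviewees". The order is free, and the interviewer has room to explore further.

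In Appendix 1, the motivation question for managers is "Are there any motivations that prompted you to support/promote this service" and for members "What are your motivations for taking part in this service". Neither guide has a counterpart on expectations.

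**The concern.** The topic tables and the instrument disagree. The guides are fully written out, and their questions are the set that every interviewee must receive, so a topic missing from them is collected only if the interviewee volunteers it or the interviewer chooses to probe.

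This matters because of how the data will be read. The analysis starts inductively from transcripts. If a manager's transcript is silent on expectations, the analysts cannot tell whether that person had none or was never asked. What the study then reports on provider expectations would depend on which interviews happened to reach the subject. The study means to use its data to adjust the CEC, and the CEC was designed top-down, so what its promoters and members expected of it is useful input.

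**Working it through.** There is no sample size, error rate or estimate to recompute. The check sets the stated topics against every scripted question.

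**Step 1. Where expectations are promised, and for whom**

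| Place | Whose expectations |
|---|---|
| 2.2 Secondary aims | users and providers |
| Qualitative Evaluation, introduction | users and providers |
| Data-sources table, manager row | managers/heads |
| Data-sources table, member row | CEC members |
| Data-sources table, cognitive-survey row | training attendees |
| Data-sources table, requester row | not listed |
| Table 3, Coherence | interviewees in general, worded around implementing the CEC |

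**Step 2. What the guides ask.** The count covers substantive questions. It leaves out opening courtesies and the closing invitation for further thoughts.

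| Guide | Opening + A + B + C + D | Total | Asks about motivations or reasons | Asks about expectations |
|---|---|---|---|---|
| Managers/heads | 1 + 4 + 2 + 3 + 2 | 12 | yes | 0 |
| CEC members | 1 + 4 + 2 + 3 + 2 | 12 | yes | 0 |
| Requesters | 0 + 3 + 3 + 3 + 2 | 11 | yes (reasons for the request) | 0 |

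For the two guides to which the data-sources table assigns the topic, the result is 0 of 12 + 12 = 24. Across all three guides it is 0 of 24 + 11 = 35. Expectations are also absent from the Coherence row that opens Appendix 1 and from the A to D theme lists of all three guides.

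**Step 3. Nearest questions in the manager and member guides.** Role and goal ask what the CEC is for. Motivation asks why the person supported or joined it. Potentials (managers) and strengths (members) ask about the service as implemented. Overall evaluation and improvement ask for a judgement and for changes. Each could lead someone to mention expectations, but none asks for them. Table 3 names motivations and expectations as a pair, and only the first became a question.

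**Step 4. Is the topic picked up elsewhere?**

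- Training attendees: yes. The protocol says the open questions of the cognitive survey are meant to elicit expectations. It also describes NoMAD as covering expectations about the service becoming routine.
- All employed professionals: the anonymous survey covers knowledge, spread, access, activities received, interest and impact. Expectations are not on its list.
- Managers and members, in those roles: the interview is the only source of opinion listed.

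The uncovered part is therefore provider expectations. The CEC has 15 members, so at most 15 member interviews are affected. Current employment is also listed among the eligibility criteria; if it is applied to the 6 external members, the ceiling is 15 − 6 = 9. The number of managers to be interviewed is not given.

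**The case against.** The strongest reply is that this is a semi-structured guide in a descriptive, exploratory study. The compulsory questions on role, goal, motivation, evaluation at 16 months and improvement come close to the subject, trained interviewers may probe, and Table 3 joins motivations and expectations with a slash, as if they were one topic. Part of this stands: the topic is not blocked, and some interviews will yield material on it. It does not close the gap. Probing is optional while the scripted set is compulsory, and the data-sources table names expectation without mentioning motivation, so the motivation question cannot simply stand in for it.

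A reader might infer three stronger things, and the documents support none of them.

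- *That all three guides fail their specification.* The data-sources table does not assign expectation to the requester interviews. For that guide the case rests only on the general aim and on Table 3, whose wording about implementing the CEC fits those who set it up better than those who sent a request.
- *That the expectations element of the secondary aim has no data source.* The cognitive survey is meant to supply it for training attendees.
- *That the study could not deliver a promised comparison of expected with experienced service, or of providers with users.* No section promises either. The data-sources table promises only to explore opinion.

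**Conclusion.** The point holds for the manager and CEC-member guides. A topic that the plan assigns to those interviews has no scripted question (0 of 24), and the plan lists no other source of opinion for these two groups in those roles. Following the plan as written would leave provider expectations without systematic data.

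The size is modest. One element of a secondary aim is affected, for two of the three interviewed groups, and nothing in the primary aim depends on it. The conclusion rests on two readings: that the Appendix 1 questions are the compulsory set the protocol describes, and that questions on role, goal, motivation and improvement do not by themselves ask about expectations. It also assumes that interviews have not begun, which fits the prospective qualitative design. The correction is worth making because it is cheap now and would need re-contact later.

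**What to change.** Before interviews start, add one scripted question to Topic A of the manager and member guides, for example: *What did you expect of the CEC when it was set up, and what do you expect of it now?* Add expectations to theme A of those two guides so that they match Table 3.

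A matching question for requesters is optional, since the data-sources table does not list the topic for them.

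Analyse the answers as section 5.3.3 already sets out: inductive thematic analysis first, with the NPT constructs applied afterwards. They should not be assigned to Coherence in advance. State in the report that expectations recalled about 16 months after set-up are open to hindsight.

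The alternative is to remove expectation from the manager and member rows and from Table 3. That would restore consistency but give up the provider half of this element of the secondary aim.

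The cost is a minor revision of the guides and a few minutes per interview. If the question takes 2 to 3 minutes (an assumption), that is between 2/50 = 4% and 3/30 = 10% of the planned 30 to 50 minutes.
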